This study evaluates the effect of a fractionated carbon dioxide laser on surgical scars of the face and neck over 12 months. Anyone with a surgical scar on the face and neck who has not had laser therapy may be eligible. The visits occur every three months for up to 12 months. Subjects will be randomly assigned to receive two high energy treatments or two low energy treatments. During the study visits, the scars will be photographed pre-treatment and the subject will complete a questionnaire to rate the scar. Three physicians will also evaluate the scar: one as a live assessment and the other two will evaluate the scars after each visit using photographs. Patients will receive their assigned treatment, obtain post-treatment instructions, and a diary to record redness, swelling, pain, itching, or other skin changes after treatment. Patients and raters will be blinded to which therapy level the patient receives until the 9-month visit (Visit #3) at which time patients will be unblinded and offered to have a third high energy treatment if in the high energy treatment group or to have two high energy treatments if in the low energy treatment group.

Study Timeline

The study will occur over 14 months. Our tentative timeline consists of recruitment and screening to occur in November 2016-September 2017. Study visits and data collection would occur between November 2016 and September 2017. Preliminary data analysis and publication of preliminary results would occur between August 2017 and March 2018. Final data analysis and publication would be between October 2018 and January 2019.

Introduction

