
If a patient prefers not to have treatment at this visit, they will be asked to return to clinic for this first treatment within 30 days from the screening and randomization visit. Subjects will return for a second treatment 3 months later. With 10 min allotted for treatment, as well as completing the patient questionnaire (5-7 minutes), assessment of adverse events and updating medications and procedures, along with performing photographs (10 min) and having an evaluation by the blinded evaluator, the entire visit may take up to 30-40 min. The diary entries will take 5 minutes each day. Subjects will return again 3 months following the second treatment and will undergo the follow up photos and assessments. Subjects will be unblinded at the third visit to the treatment received and given three options. One option is to exit from the study. The second option is if the subject received the high energy laser treatments, the subject may elect one additional treatment that day. The third option is subjects with low energy treatments have the option to receive two high energy treatments at this visit and a subsequent visit. Those in the high energy group who receive the third optional high energy treatment will return in 3 months for an exit visit and follow-up assessment of the scar (photos, patient POSAS, and observer POSAS) and exit at visit #4. Those in the low energy group who elect the two high energy treatments will follow up in 3 months after Visit #3 for the final high energy treatment, photos, and assessments (patient POSAS and observer POSAS). After receiving the last optional high energy treatment at Visit #4, patients in this low energy treatment group will return to the clinic in 3 mos for the last study visit where pictures will be obtained, survey assessments of the scar will occur, and the

subject will exit from the study. This allows comparison of all subjects following 2 treatments, and adds further data to the high energy laser treatment group for subjects who cross over.

The subjects' participation may be up to 14 months.

Visit Flowchart

Study Visit #1

The subject will verify information regarding the subject's name and contact information. The subject cannot take part in this study if the subject has a history of prior laser treatment to the face or neck, or if

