This visit occurs 3 months after the subject's second treatment with the following activities:

- The subject will return the diary
- The subject will complete a questionnaire
- o The subject will undergo scar evaluation by the research physician
- The subject will have photographs taken
- The treating investigator will let the subject know which treatment the subject received
- o If the subject received the high energy laser treatment, the following will occur:
 - The subject will be offered the option to receive a third high energy treatment.
 - If the subject accepts treatment today, the subject will return in 3 months for the final follow up visit and to exit the study
- o If the subject declines further treatment, the subject will be exited from the study at this visit.

If the subject received the low energy laser treatment, the following will occur:

- The subject will be offered the option to receive two high energy treatments.
 - o If the subject accepted treatment, the subject will receive one treatment today and return in 3 months for the second treatment (Visit 4); the subject will then be asked to return 3 months later for a follow up final study visit (Visit 5).
- o If the subject declined further treatment, the subject will be exited from the study.

Study Visit #4

If the subject were originally treated with the high energy laser, and elected a third treatment at Visit 3, this visit occurs 3 months after the subject's Visit 3 treatment with the following activities:

- The subject will return the subject's diary
- o The subject will complete a questionnaire
- The subject will undergo scar evaluation by the research physician
- The subject will have photographs taken
- The subject will be exited from the study

If the subject were originally treated with the low energy laser, and elected treatment with the high energy laser, this visit occurs 3 months after the subject's Visit 3 treatment with the following activities:

- o The subject will complete a pre-treatment questionnaire
- The subject will receive the last high energy laser treatment The subject will obtain post-treatment instructions
- The subject will obtain a paper diary to record possible reactions such as redness, swelling, pain, itching or color changes following treatment

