Patients who require evaluation outside of the three month windows +/- two weeks due to a related adverse event will be evaluated by the research team at the earliest convenience. If the nature of the evaluation is in regards to an adverse event/significant adverse event, a severe cutaneous reaction to the laser, or having an unrelated cosmetic procedure involving the study scar during the study, staff will evaluate the patient accordingly, document the event, and report any serious adverse events to the SLU IRB within a 24 hour window.

Completion of Study

At the completion of the study, the data obtained will be reviewed and analyzed with the aid of the Saint Louis University Center for Health Outcomes Research. This data will then be presented in the form of a paper and/or scientific poster. At the completion of the study, the data obtained will be presented in the form of a scientific paper and/or scientific poster.

Methods of Assigning Subjects to Treatment Arms

In terms of randomization, a spreadsheet will be created by the principle investigator with the aid of the research staff to predesignate the treatment assignment. For each patient that comes in, the principle investigator will use that as a guide to dictate the treatment arm assigned for that subject.

Blinding

Other than the investigating physician performing the laser treatment, no one (including the subjects, study coordinators, and the physicians who will be evaluating the response to treatment) will know who is receiving the high energy treatment or the low energy treatment until Visit #3.

Unblinding

At the Visit #3, subjects and the investigating physician performing the treatments will know the type of treatment that the subject in question received.

Concomitant Treatments

Prohibited

Patients will be prohibited from obtaining any additional cosmetic procedures during the study (i.e. dermabrasion, chemical peels) that may interfere with the interpretation of the results of the study.

Permitted

Patients will be permitted to continue using the moisturizers and cleansers that they have been using for the last 6 months. Patients will be allowed to take all oral medication (except isotretinoin) throughout the study.

Benefits and Alternatives

Benefits

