As soon as the PI becomes aware of an AE that meets the criteria for an SAE, the SAE should be documented to the extent that information is available. A report must be submitted by the study site to the SLU IRB, within 24 hours. Forms for reporting SAEs will be provided to the study site. SAEs will be recorded from the time of informed consent, through the end of the study. If in the opinion of the Investigator, an SAE occurring outside the specified time window (i.e., following subject completion or withdrawal from the study), is deemed to be device related, then the event should be reported with 24 hours as outlined above. The Investigator should institute any clinically necessary supplementary investigation of SAE information.

Death

In the case of subject death, any post-mortem findings/reports will be requested and a report (even if a preliminary diagnosis/cause of death is available) will be submitted to the SLU IRB within 24 hours of learning about the death.

Reporting of Pregnancy

In the case of subject pregnancy, the subjects will be discontinued from the study and will be followed leading up to delivery.

Data Analysis and Statistical Considerations

At the completion of the study, the data obtained will be reviewed and analyzed with the aid of the Saint Louis University Center for Health Outcomes Research. A chi-square test along with the Wilcoxon signed rank test will be performed to assess significant difference between clinical improvement scores between study visits. There is no data to suggest that there is a difference in the appearance of older (more than 1 year old from the initial injury) and newer scars post-therapy. We will aim to recruit 20 patients with old scars (10 of which will be in the high energy treatment group, and 10 of which will be in the low energy treatment group). In terms of statistical analysis, we will review whether there is a difference between the post-treatment measurements and appearance of older scars and newer scars.

Quality Control and Quality Assurance

Quality control and assurance for this study will be performed by an internal review every 3 months to ensure that the data collected is in accordance with the goals of this study and to address any issues with data collection or performance of any study procedures.

Direct Access, Data Handling and Record Keeping

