Access to all study materials will be kept in a locked facility within the SLU Dermatology Des Peres Office. Only staff members will have access to this room. With respect to the randomization spreadsheet, only the principle investigator will have access to this information. This information will be kept in a locked file cabinet in her office. The source documents created by the study site will be the primary forum for recording study data. When the study is completed, these documents will be placed in a long term storage facility owned by SLU.

Confidentiality

Interested subjects will sign a HIPPA form allowing access to relevant medical records. All study data will remain confidential, unless it is deemed by the principle investigator and/or research team members that it is important for the patient's health for study participation to be disclosed to appropriate parties (i.e. other medical providers). Study materials for each subject will have a deidentified code, such as subject Jane Doe is subject 001.

Data Protection

The master list, which will be password-protected, will be kept confidential to all research staff except the principle investigator. She will be the only unblinded individual in this study who will set the password for this document and will have access to the master list. Study materials for each subject will have a deidentified code, such as subject Jane Doe is subject 001.

Records Retention

Records will be retained within a locked office within the SLU Dermatology Des Peres Office

Posting to Clinical Trials Register and Publication

Information about this study will be posted to the Clinical Trials Register (accessible via http://www.clinicaltrials.gov). Recruitment for the study will be open until the study has obtained 50 patients. All recruitment information posted to the Clinical Trials Register will be reviewed and approved by the SLU IRB. Final data analysis and publication will be between July and August 2017.

References

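### The analysis section states no high versus low energy comparison, no analysis visit and no rule for records after Visit 3, yet crossover records are said to add to the high energy group

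*Combined protocol and SAP*

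**What the plan says.** The opening summary and Dose Regimen describe two randomised arms, each given two sessions of high or low energy laser.

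**Analysis.** Data Analysis and Statistical Considerations names a chi-square test and a Wilcoxon signed rank test "to assess significant difference between clinical improvement scores between study visits". It then promises a review of older against newer scars. It does not mention energy level as a contrast, a visit for the main analysis, or the handling of Visits 4 and 5.

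**Crossover.** Under Study Procedures, low energy subjects may choose two high energy sessions from Visit 3 on, and high energy subjects may choose a third. That section says of the design: "This allows comparison of all subjects following 2 treatments". The same sentence goes on to say that it "adds further data to the high energy laser treatment group for subjects who cross over".

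**Blinding.** The Blinding section says that nobody except the treating physician "will know who is receiving the high energy treatment or the low energy treatment until Visit #3". Unblinding says that at Visit 3 "subjects and the investigating physician performing the treatments will know the type of treatment". Data Protection says of the principal investigator: "She will be the only unblinded individual in this study". Of the three rating physicians, one sees the scar live and, per the summary, "the other two will evaluate the scars after each visit using photographs".

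**The concern.** Energy level is what the trial randomises, and the analysis section does not say how it will be compared. The signed rank test is paired, so it cannot compare two independent arms. A chi-square test could, but the text ties it to differences between visits.

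The crossover clause fills that gap with the only guidance on later records, and the guidance points to the high energy group. An analyst following it could add Visit 5 records from low energy subjects to the high energy side. The comparison would then no longer be randomised. Effects of elapsed time, extra sessions, knowledge of treatment or self-selection would be read as an effect of energy level.

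**Working it through.** The plan gives no alpha, power, SD, allocation ratio or crossover uptake, so there is no figure of its own to reproduce. The finding rests on the text; the numbers only show scale.

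**1. What a crossover record is.** With sessions at months 0 and 3, Visit 3 falls at month 6, Visit 4 at month 9 and Visit 5 at month 12. With the permitted 30-day delay these become about months 7, 10 and 13. At Visit 5 a crossover subject:
- has had 2 low + 2 high = 4 sessions, against 2 for a high energy subject at Visit 3;
- is 12 − 6 = 6 months past Visit 3;
- chose the treatment after learning the arm;
- already supplies a low energy record at Visit 3, so would sit on both sides of a pooled comparison.

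**2. What is blinded after both assigned sessions.** The Visit 3 list places the questionnaire, live evaluation and photographs before the step "The treating investigator will let the subject know which treatment the subject received". Visit 3 is therefore the only blinded scar assessment after both assigned sessions. The 30-day diary kept after the second session is also blinded and also follows both.

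**3. Share of scars maturing between Visits 3 and 5.** Inclusion and Exclusion Criteria puts maturity of most scars at 1 year and aims for 20 older scars among 50.
- Younger scars: 50 − 20 = 30, or 60%.
- Assume enrolment age uniform over 8–51 weeks (44 values). Scars aged 8–25 weeks at enrolment are under 52 weeks old at Visit 3 (+26 weeks) and at least 52 at Visit 5 (+52 weeks).
- 18/44 = 41%; 0.41 × 0.60 ≈ 25% of all scars. With a delay of about 4 weeks it is 14/44 = 32%, or 19% of all.

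**4. Bias if crossover records are pooled.** Assume 25 per arm, no true arm difference, uptake unrelated to outcome, and a 0.5 SD gain in the 25% that mature. With k crossover records:

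bias = k/(25 + k) × (0.25 × 0.5 + extra shift)

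The extra shift stands for additional sessions or open-label rating and is assumed. The false-positive rates come from simulation (20,000 runs per cell, within-subject correlation 0.5, two-sided rank-sum test at 0.05).

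| k | share k/(25+k) | bias, no extra | rate | bias, +0.3 SD | rate | bias, +0.5 SD | rate |
|---|---|---|---|---|---|---|---|
| 6 | 19% | 0.02 | 4.0% | 0.08 | 4.6% | 0.12 | 5.7% |
| 12 | 32% | 0.04 | 3.2% | 0.14 | 5.4% | 0.20 | 8.5% |
| 25 | 50% | 0.06 | 2.2% | 0.21 | 8.2% | 0.31 | 17.4% |

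Example: 25/50 × (0.125 + 0.5) = 0.3125 SD. Rates fall below 5% when the shift is small because the same subjects sit in both groups. The Visit 3 test by assigned arm stays at 4.4–4.9%.

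**5. Self-selection.** With k = 12, 25% maturing and no extra shift, bias is −0.09 SD if the 12 worst low energy scars cross over (rate 3.9%) and +0.17 SD if the 12 best do (6.7%).

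**The case against.** The strongest reply is that nobody has written a pooled analysis. The crossover clause is one descriptive remark outside the analysis section, and its sentence first speaks of comparing everyone after two treatments, which most naturally means Visit 3. The planned between-visit tests would also treat crossover records as within-subject change, close to what is recommended here. This stands as a limit: a reader might infer that the sponsor will pool, and the documents do not show that. It does not remove the gap. The clause names no visit, endpoint or test. It could also mean Visit 5 for crossover subjects, after their two high energy sessions.

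The second reply is that the numbers are modest and depend on stacked assumptions. That is fair. Maturation alone inflates nothing, and at 0.3 SD extra shift only full uptake goes clearly above 5%. Nor may one assume that every younger scar matures between Visits 3 and 5: on the protocol's own timing, 44 − 18 = 26 of the 44 possible enrolment ages are already at 52 weeks or more by Visit 3.

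A reader might also infer that photograph raters lose their mask at Visit 3. The Blinding wording permits that, but the Unblinding section names only subjects and the treating physician, the Visit 3 list puts ratings before disclosure, and Study Procedures refers to a blinded evaluator. This is a matter of wording.

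**Conclusion.** The point holds as an omission in the analysis plan, and should be fixed before data are seen. The randomised contrast has no stated comparison, visit or suitable test, and the one sentence on crossover records points towards a use that would break randomisation. Confidence is high on the absence and lower on the harm, which arises only if the records are pooled in an arm comparison.

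Its size ranges from no inflation to a false-positive rate of about 17%. The upper end needs all 25 low energy subjects to cross over and 0.5 SD of extra shift on top of maturation. The arm size, correlation, test, uptake, maturation and shift are all assumptions. Because self-selection can turn the bias either way, it cannot be reliably corrected afterwards.

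**What to change.** Add to Data Analysis and Statistical Considerations:

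> The randomised comparison is high versus low energy by assigned arm, each subject once, on change from baseline to Visit 3 in POSAS and Vectra measurements, using assessments obtained before the subject is told the arm, with a test for independent groups (for example the Wilcoxon rank-sum test). Tolerability is compared by assigned arm from the diaries after the first two treatments. Records after Visit 3, including third high energy treatments and crossover treatments, are reported separately as open-label, within-subject results and are not pooled with the randomised high energy arm.

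Qualify the crossover clause in Study Procedures to match.

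Minor wording to settle at the same time:
- State that photograph raters stay masked to arm when scoring Visit 3 and later images.
- Reconcile the opening summary, Study Procedures, Study Visit #3, Blinding, Unblinding and Data Protection on who is unblinded and when. The Data Protection sentence needs qualifying too, since subjects are also told their arm at Visit 3.
- Reconcile the summary's nine-month label for Visit 3 with the visit schedule, which puts it at about month 6 to 7.

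**Cost.** A few sentences, with no added visits, patients or measurements. The high energy arm stays at its randomised size, and crossover data support only open-label statements. With an assumed 25 per arm, two-sided 0.05 and no dropout, a normal approximation gives 80% power for (1.96 + 0.84) × √(2/25) ≈ 0.79 SD.

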 - Expect the treated area to be red for several weeks. You can use makeup starting three days after the treatment, but it is best to wait until the skin has fully exfoliated and becomes pink to red shiny, smooth skin. This usually takes 7 to 10 days.
 - Some swelling may develop, and generally lasts 1-2 days. It is recommended that you sleep in a slightly elevated position to help relieve swelling.
 - It is common to feel a heat or sunburn sensation in the treated areas. This heat will dissipate over the next few hours. Cold compresses, such as ice, may help soothe the heat and can be gently applied to the skin.
 - Pain is uncommon after the first few days, and usually subsides with Tylenol and cooling the skin. Itching can be seen, and will usually last a few days or less. You can press on the clean itchy skin with a cotton tipped applicator (i.e. Q-tip) to relieve the itching. Avoid scratching the skin.
 - Normal daily activities may be resumed immediately after treatment. Avoid strenuous exercise, bending, straining, stooping or lifting heavy objects for 48 hours. These activities may cause swelling and pain in the treatment area. If a patient is not able to receive the treatment on the same day as the screening and randomization visit (possibly due to an ongoing oral herpetic infection), they may return to the office within 30 days for their first treatment.

Study Visit #2

The subject will be asked to return in 3 months for a second treatment visit with the following activities:

- The subject will complete a pre-treatment questionnaire
- o The subject will receive laser treatment as randomized to high energy or low energy treatment
- The subject will obtain post-treatment instructions
- The subject will obtain a paper diary to record possible reactions such as redness, swelling, pain, itching or color changes following treatment
- If the subject has a history of recurrent fever blisters/cold sores on the lips or face, the subject will be offered a three day prescription for an antiviral medication that the subject can fill at the subject's pharmacy to prevent a recurrence since laser treatments may increase the chance of recurrent episodes. The subject would take one pill every twelve hours the day prior to

treatment, on the treatment day, and the first day post-treatment. The subject or their insurance plan must cover the cost of the medication. This may delay the treatment to a later date within 30 days of the screening visit.

Study Visit #3

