- o If the subject has a history of recurrent fever blisters/cold sores on the lips or face, the subject will be offered a three day prescription for an antiviral medication that the subject can fill at the subject's pharmacy to prevent a recurrence since laser treatments may increase the chance of recurrent episodes. The subject would take one pill every twelve hours the day prior to treatment, on the treatment day, and the first day post-treatment. The subject or the subject's insurance plan must cover the cost of the medication. This may delay the treatment to a later date within 30 days of the screening visit.
- The subject will be asked to return in 3 months for a final follow- up visit

Study Visit #5

This visit occurs 3 months after the subject's last treatment if the subject received the low energy laser treatment followed by the high level laser therapy as a final study visit. The subject will not be offered treatment at this follow up visit. The following will occur:

- The subject will return the subject's diary
- o The subject will complete a questionnaire
- o The subject will undergo scar evaluation by the research physician
- The subject will have photographs taken.

At any time, the subject may choose to not participate in the study. If the date that they elect to discontinue from the trial occurs shortly after a treatment (within minutes to 30 days after treatment), patients will be asked to return for a follow-up 3 months to evaluate for any significant adverse events. No treatments will be performed. Only photographs of the scar and rating of the scar by the patient and evaluators will be performed at this visit. Also, collection of the diary will occur at this visit. If subjects discontinue from the trial after 30 days, patients will be followed up via phone for the reason of their discontinuation and to assess for AE/SAEs and asked to return the diary as soon as possible. In either case, subjects will be given the contact information for the research office in case they have further concerns regarding their participation in the trial.

Unscheduled Visits

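### Visit 3 gives the optional laser on the day it is offered, with no cold-sore antiviral step or deferral, and the antiviral delay limit at Visits 2 and 4 has already expired

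*Combined protocol and SAP*

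**What the plan says.** The combined protocol and SAP offers a three-day antiviral prescription to subjects with recurrent cold sores, because laser may provoke a recurrence. The timing is explicit: "The subject would take one pill every twelve hours the day prior to treatment, on the treatment day, and the first day post-treatment". The offer appears in the Study Procedures account of the screening and first-treatment visit, and in the lists for Study Visit #1, Study Visit #2 and Study Visit #4 (low energy subjects who cross over). Each time it is followed by the same limit: "This may delay the treatment to a later date within 30 days of the screening visit".

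Study Visit #3 is also a treatment visit for anyone who accepts the offer made on unblinding. For the low energy arm, "the subject will receive one treatment today and return in 3 months for the second treatment (Visit 4". For the high energy arm, "If the subject accepts treatment today, the subject will return in 3 months for the final follow up visit and to exit the study", and Study Procedures says "the subject may elect one additional treatment that day". None of this text mentions the antiviral or a later treatment day.

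**The concern.** The plan adopts a protection that needs one day's lead time. At Visit 3 the subject learns the arm, decides, and is treated in one sitting, so a subject who follows the text as written has had no day-before dose. The plan's reason for the antiviral applies at Visit 3 as much as at the other treatment visits.

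At Visits 2 and 4 the offer sits in the treatment visit's own list. A subject first given the prescription there needs a short delay, and the only delay the text allows ended months before. Staff must either treat without the first dose or depart from the written limit.

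What is at stake is participant protection and consistent conduct across visits, not inference.

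**Working it through.** The plan gives no figure to reproduce, so the check compares the visit lists and then counts days.

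**Visit lists**

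| Visit | Laser | Antiviral offer | Delay limit | Usable? |
|---|---|---|---|---|
| 1 | Assigned energy | Yes | 30 days from screening | Yes |
| 2 | Assigned energy | Yes | 30 days from screening | No |
| 3 | Optional, high energy, same day | No | None | n/a |
| 4 (low energy crossover) | High energy | Yes | 30 days from screening | No |

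- High energy subject who takes the third treatment: 3 treatments, 2 with the antiviral step, 1 with a usable limit.
- Low energy subject who crosses over: 4 treatments, 3 with the step, 1 with a usable limit.

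**Inputs for the day count**

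- First treatment on day 0 to 30 after screening (Study Procedures).
- Later visits 3 months after the preceding treatment (Study Procedures; Study Visits #2 to #5). I take 3 months as 91 days.
- A window of 14 days either way, mentioned under Unscheduled Visits. Applying it to every scheduled interval is my assumption.

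**Nominal gaps past the day-30 limit**

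1. Visit 2 = (0 to 30) + 91 = day 91 to 121. Gap = 91 − 30 to 121 − 30 = **61 to 91 days**.
2. Visit 4 = (0 to 30) + 3 × 91 = day 273 to 303. Gap = 273 − 30 to 303 − 30 = **243 to 273 days**.

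**Smallest gaps, every interval shortened by 14 days to 77**

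3. Visit 2: 77 − 30 = **47 days**.
4. Visit 4: 3 × 77 − 30 = 231 − 30 = **201 days**.

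The limit cannot be met at either visit under either assumption.

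**Does other text fill the Visit 3 gap?**

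The Visit 3 list is abbreviated and also omits the diary and eye shields. General text supplies those: the diary follows each treatment (Study Objectives) and eye protection is given during treatment (Safety). Three passages might do the same for the antiviral, but none does:

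- The Study Procedures offer describes the screening and first-treatment visit and carries the same 30-day limit.
- The return allowance for an active oral herpes infection, at the end of Study Visit #1, covers the first treatment only.
- The acyclovir text under Safety lists reactions and assigns the drug to no visit.

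A three-day prescription covers one treatment, so the one issued for Visit 2 does not carry over to Visit 3.

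**The case against.** The strongest reply is that these are drafting slips with an obvious intended meaning. Cold-sore history matters from Visit 1, Visits 2 and 4 are planned treatment visits, and nothing stops staff prescribing ahead. The two-week window under Unscheduled Visits implies that scheduled visits have some latitude, and a shift of one or two days for pre-dosing would fit inside it. A figure under Study Procedures is also missing from the text available, and its content is unknown.

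Much of this stands, and it keeps the point minor. It does not remove it. The window is mentioned only for evaluations prompted by a related adverse event and is not offered as a deferral for prophylaxis. Nothing tells staff to prescribe ahead. The written lists conflict with the dosing schedule whatever the missing figure shows.

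A reader might infer three stronger claims that the documents do not support:

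- **That the plan forbids prophylaxis at Visit 3.** It is silent, and the site could provide it.
- **That every subject with this history should pre-dose before Visit 3.** The subject decides only after unblinding at that visit. Anyone who then declines would have paid for the drug and been exposed to it without need, and Safety lists rare but serious acyclovir reactions.
- **That the stated participation limit ("The subjects' participation may be up to 14 months") sets a firm maximum for antiviral delays.** Any such maximum depends on a zero visit window. With 14 extra days on each of four intervals, exit is already day 30 + 4 × 105 = 450, beyond 14 × 30.4 = 425.6 days, before any delay.

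**Conclusion.** The point holds as a minor participant-safety procedure error in two parts: a missing antiviral step and deferral at Visit 3, and an expired delay limit at Visits 2 and 4. That the limit has expired does not depend on the assumed length of a month or on the window, since the smallest gaps are 47 and 201 days. The Visit 3 part rests on the text as available.

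The consequence is limited. It concerns only subjects with recurrent cold sores. The Visit 3 laser and the antiviral are both optional, and Safety describes infection as mild. The documents give neither the share with this history nor the share who accept the Visit 3 offer, so no count of affected subjects is possible.

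A reader might also infer a threat to the efficacy result. The documents do not support that: the Visit 3 assessments and unblinding belong to the end of the randomised phase, the optional laser comes after it, and the Visit 2 wording is the same in both arms.

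**What to change.** For subjects with a recurrent cold-sore history:

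1. **Visit 3.** Add the antiviral offer to the list and allow the optional treatment on a later day, for example within one week, so that dosing follows the subject's decision.
2. **Visits 2 and 4.** Issue the prescription at the preceding visit. Replace the limit with a short one tied to that visit's own date, for example up to one week.
3. **Consequential edit.** Study Procedures says low energy subjects who cross over "will follow up in 3 months after Visit #3 for the final high energy treatment", whereas the Study Visit #4 list says "this visit occurs 3 months after the subject's Visit 3 treatment". The two agree while treatment is given on the day of Visit 3. Once deferral is allowed, use the second. Otherwise a 7-day deferral shortens the interval between the crossover treatments from 91 to 91 − 7 = 84 days.

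The investigator should confirm the regimen.

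The cost is a small amendment, an occasional extra treatment day and a small shift in later visits. With exact 91-day intervals, the latest crossover exit is 30 + 4 × 91 = day 394. A full week's delay at Visits 2, 3 and 4 makes it 394 + 21 = day 415, inside 14 months (about 426 days). For a high energy subject with a third treatment and a week's delay at Visits 2 and 3, exit is 30 + 3 × 91 + 14 = day 317. If visits may also run late by up to two weeks each, the 14-month figure needs separate attention whether or not this change is made. No extra patients are needed.
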